6.1.3. Protocol Deviations

All protocol deviations, important protocol deviations and protocol deviations which will lead to exclusion from PP population will be summarized. Protocol deviations will also be listed for the MITT population.

Protocol deviations will be tracked by the study team throughout the conduct of the study. These protocol deviations will be reviewed to identify those considered as important as follows:

- Data will be reviewed prior to unblinding and freezing the database to ensure all important deviations (where possible without knowing the study intervention details) are captured and categorised in the protocol deviations dataset.
- This dataset will be the basis for the summaries of important protocol deviations.

Protocol deviations which result in exclusion from the analysis set will also be summarized.

- Data will be reviewed prior to unblinding and freezing the database to ensure all deviations leading to analysis population exclusions are captured and categorised in the protocol deviations ADaM dataset (note these exclusions are not captured in the SDTM dataset).]

In addition to the overall summary of important protocol deviations, separate summaries will be produced for important protocol deviations related to COVID-19, and important protocol deviations not related to COVID-19 respectively.

The date of and the reason for breaking the study blind will be listed for the MITT population.

6.1.4. Prior and Concomitant Medications

The proportion of subjects reporting each concomitant medication will be presented. Multi-ingredient medications will be presented according to their combination ATC classification rather than the classifications of the ingredients. Summaries will be split into asthma and non-asthma concomitant medications, as well as into those taken pre-treatment, during treatment and post-treatment. Asthma medications will be grouped for Respiratory Medications Classes as well, which are based on pre-defined code lists derived from ATC classifications:

- Androgens and Estrogens
- Anti-IgE, Anti-IL5
- Antiinfectives (antibiotics, antiseptics)
- Antimycotics
- Antivirals
- Beta 2 Agonist
- Corticosteroid
- Leukotriene Receptor Antagonist
- Long-acting anticholinergic

- Long-acting beta-2 agonist – Group 2 (Once per day)
- Long-acting beta-2 agonist – Group 3 (Twice per day)
- Mucolytics
- Nedocromil or Cromolyn Sodium
- Oxygen
- PDE4 Inhibitors
- Short-acting anticholinergic
- Short-acting beta-2 agonist
- Theophylline
- Xanthine

Classification of a medication as pre-, on- or post-treatment will be made with reference to the study treatment start and stop dates and the medication start date. If the medication start date is missing or partial then the medication will be considered on-treatment unless there is evidence to the contrary (e.g. the month of the start date is present and is less than the month of the first dose of study medication). Medications with a start date of up to 4 weeks after the last dose of treatment will be considered on-treatment. Medications with a start date after this period will be considered post-treatment.

Pre- and on-treatment respiratory medications will be summarised separately.

A medication will be summarised in every period (pre/on-/post) in which it was taken, so a medication that was started in the run-in and stopped during active treatment will appear in both the pre-treatment and the during treatment tables.

The listings of all asthma and non-asthma concomitant medications will be provided.

6.1.5. Study Intervention Compliance

A summary of treatment compliance is not applicable to this study; however number of treatments received is summarised in the Extent of Exposure Section 4.5.1.

6.2. Appendix 2 Data Derivations Rule

6.2.1. Planned and Actual Treatment

For participants who received the correct treatment throughout the study, the actual treatment will be the same as the planned treatment. For participants who received an incorrect treatment, the actual treatment will be derived as follows:

- If the number of doses on an incorrect treatment is less than the number of doses on the planned treatment then the actual treatment is assigned as planned treatment.
- If the number of doses on an incorrect treatment is equal to or greater than the number of doses on the planned treatment then the actual treatment is assigned as the incorrect treatment.

6.2.2. Analysis Period for Exacerbations and Efficacy Endpoints

The analysis period defines the period of time over which exacerbations and efficacy assessments will be included in the on and/or off-treatment phases. The start and end of the analysis period is defined for subjects based on their study completion status as follows:

Study Completion	Start Date of Analysis Period	End Date of Analysis Period
Completed	First dose of investigational product (Day 1)	Earlier of Date of Week 52 visit or Date of last dose at Week 48 +35 days [1]
Withdrew early	First dose of investigational product (Day 1)	Earlier of Date reported on the study conclusion page or Date of last dose at Week 48 +35 days [1]

[1] Based on protocol Section 4.1, the Exit Visit (Visit 15) represents the last day of study (i.e. 4 weeks after the last dose given at Visit 14), allowing for the ± 7 days visit window, date of last dose at week 48+35 days is defined as the upper bound of 7 days visit window for the date of last dose at week 48+28 days.

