
 Least-square (LS) means and LS mean change from baseline values for each treatment group will be presented with their associated standard errors as well as 95% CIs. The estimated treatment difference along with corresponding standard error, 95% CI for each Visit will be presented.

Endpoint / Variables

 The LS mean treatment differences (and associated 95% CIs) for all visits will also be presented graphically.
Missing data imputation
The analysis using the MMRM model assumes that missing data is missing at random (MAR).
Sensitivity and Supportive Analyses

 The sensitivity analyses of the repeated measures analyses will be performed for the FEV1 key secondary endpoint using multiple imputation methods under MAR based on pattern mixture models. The method is analogous to the multiple imputation of exacerbation events. A supportive analysis of the repeated measures pre-bronchodilator FEV1 analysis will be performed, excluding all values captured within 6 hours of a SABA being administered or 12 hours of a LABA being administered to the subject. Another supportive analysis will be repeated using the “Per-protocol” analysis population
Additional estimands
A supplementary analysis will be performed using the “treatment policy” strategy for the intercurrent event of discontinuation of treatment. This analysis will include both on-treatment and off-treatment value. For missing data imputation, the missing data are assumed as MAR.

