4.4. Other Analyses

Endpoint(s)

 Mean change from baseline compared to placebo in Asthma Control Questionnaire (ACQ-5) score at Week 52 The ACQ-5 is a 5-item questionnaire developed as a measure of patient's asthma control. Response options for each question are on a 7-point scale ranging from 0 (CCI [REDACTED]) to 6 (CCI [REDACTED]). The questions are equally weighted, and the ACQ-5 score is calculated as the mean of the 5 questions, ranging between 0 (CCI [REDACTED]) to 6 (CCI [REDACTED]), where higher scores indicate worse asthma control. Mean change from baseline in clinic post-bronchodilator FEV1 at week 52
Model Specification, Checking & Diagnostics, Results, Presentation

 MMRM These endpoints will be analyzed using a mixed models repeated measures analysis (MMRM) adjusting covariates: baseline, baseline maintenance OCS therapy (OCS vs. no OCS), exacerbations in the year prior to the study (as an ordinal variable), baseline % predicted FEV1, treatment and visit, plus interaction terms for visit by baseline and visit by treatment group. A dataset om_dataset will be constructed to reflect the data structure of no missing observations

Missing data imputation

For a given visit, if the response to one of the 5 questions is missing then the ACQ-5 score will be calculated as the mean of the available responses. If the response to more than one question is missing, then the ACQ-5 score will be set to missing.
 
The analysis using the MMRM model assumes that missing data is missing at random (MAR).

Endpoint(s)

 Percent of subjects evaluated as responders as measured by ACQ-5 score at Week 52 ACQ-5 score responder is defined as the participant achieving a ≥ 0.5-point improvement (decrease) from baseline in ACQ-5 score. Percent of subjects evaluated as responders as measured by SGRQ score at Week 52 SGRQ responder is defined as ≥ 4 points improvement (decrease) from baseline in total score.
Missing data imputation
Subjects with missing values at Baseline will be excluded from analyses. Any missing values at post-baseline visit will be included as non-responders.
Model Specification, Checking & Diagnostics, Results, Presentation

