
 Analysis will be performed using a logistic regression model adjusting for baseline, treatment group, baseline maintenance OCS therapy (OCS vs. no OCS), number of exacerbations in previous year (as an ordinal variable), baseline disease severity (as % predicted FEV1) and baseline score. For the baseline covariate, if the factor of baseline covariate fails to converge, it will be removed from the logistic model. If the model fails to converge, e.g. due to the limited event number, then the endpoints will be analysed by Fisher exact test only. The number and percentage of patients identified as responders, non-responders or with missing data at Week 52 will be displayed for each treatment group. The model estimated ratio of the odds of being a responder in the mepolizumab treatment group compared to placebo will be presented with 95% confidence intervals and the associated p-value.

Endpoint(s)

 Percent of subjects recording a favorable treatment response as measured by the Subject Rated Response to Therapy at Week 52. Percent of subjects evaluated as having a favorable treatment response as measured by the Clinician Rated Response to Therapy at Week 52
Missing data imputation

 Subjects with missing values at Week 52 will not be imputed and will be included in the analysis as category of significantly worse.

Endpoint(s)
Model Specification, Checking & Diagnostics, Results, Presentation

 These endpoints will be analyzed using a proportional odds model (multinomial (ordered) logistic generalized linear model), with terms for treatment group, baseline maintenance OCS therapy (OCS vs. no OCS), number of exacerbations in previous year (as an ordinal variable), baseline disease severity (as % predicted FEV1). The number and percentage of patients identified as each category (including missing data) at Week 52 will be displayed for each treatment group. The model estimated ratio of the odds of being a responder in the mepolizumab treatment group compared to placebo will be presented with 95% confidence intervals and the associated p-value.

Endpoint(s)

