6.2.3. Study Period

Assessments and events will be classified according to the time of occurrence relative to the study treatment period.

Study treatment period for Exacerbation

Treatment period	Definition
Pre-Treatment	Event start date < IP start date
On-Treatment	Subjects who did not withdraw early from IP: Event onset date is on/after IP start date & on/before the end of analysis period. (IP Start Date \leq Event Start Date \leq end of analysis period) Subjects who withdrew early from IP: Event onset date is on/after IP start date & on/before the earlier of the IP stop date+28 days/end of analysis period. (IP Start Date \leq Event Start Date \leq IP Stop Date + 28 days/end of analysis period)
Off-Treatment	Event onset date is after IP stop date +28 days and on/before the end of analysis period. (IP Stop Date + 28 days < Event Start Date \leq end of analysis period)
Post-Treatment	Event onset date is after the end of analysis period. (Event Start Date > end of analysis period)

Note: the IP stop date is missing or the event start date is missing then the event considered on-treatment

Study Treatment Period for Visit Based Efficacy Assessments

Applicable to all visit-based efficacy assessment such as FEV1, SGRQ, ACQ, Subject Rated Response to Therapy, Clinician Rated Response to Therapy.

Treatment period	Definition
Pre-Treatment	Visit date < IP start date
On-Treatment	Subjects who did not withdraw early from IP: Visit date is after IP start date & on/before the end of analysis period. (IP Start Date < Visit Date \leq end of analysis period) Subjects who withdrew early from IP: Visit date is after IP start date & on/before earlier of the IP stop date +28 days/end of analysis period. (IP Start Date < Visit Date \leq earlier of IP Stop Date + 28 days/end of analysis period)
Off-Treatment	(IP Stop Date + 28 days < Visit Date \leq end of analysis period)
Post-Treatment	Visit Date > end of analysis period

Study treatment Period for Adverse Events

Treatment period	Definition
Pre-Treatment	Event start date < IP start date
On-Treatment	IP start date \leq Event start date \leq IP stop date +28 days
Post-Treatment	Event start date > IP stop date +28 days

Note: the IP stop date is missing or the event start date is missing then the event considered on-treatment

Study Treatment Period for Visit Based Safety Assessments

Applicable to all safety assessment such as vital signs, ECG, laboratory assessments:

Treatment period	Definition

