6.2.6. Assessment Window

Clinic visits are scheduled to take place as specified in the protocol. Measurements outside visit windows will not be excluded from analyses on any population. For all clinic visits, nominal visit days and times will be used for reporting, such that if a subject recorded values on the Week 4 visit that were actually made on Week 3 of treatment, they will be presented as Week 4 values.

If a subject withdraws at a scheduled visit, and these data were scheduled to be collected at that visit, the data will be summarised and analysed (as appropriate) together with data from subjects who did not withdraw. If a subject withdraws at a scheduled visit at which these data were not scheduled to be collected, or if a subject withdraws between scheduled visits, data will be slotted to the next visit where the data was scheduled to be collected according to the study flowchart. The protocol visit windows of ± 7 days should be applied to the assignment of withdrawal visits, so that if a subject withdraws within the appropriate number of days from the last visit where that data was scheduled to be collected, they would get that data slotted to that visit and otherwise the data will be slotted to the next scheduled visit. The early withdrawal visit will then be re-labelled as the corresponding visit.

For unscheduled visits, excluding a subject's baseline visit (where IP is initiated) or exit visit, the same logic will be applied. If a subject has an unscheduled assessment within the appropriate number of days (± 7 days) from a visit where that data was scheduled to be collected, this data would be slotted to that visit and otherwise the data will be slotted to the next scheduled visit. Liver event and log visits will be excluded from summary tables, but included in the 'any time post baseline' data.

If there is more than one assessment associated with a particular visit interval then the closest assessment will be used for summary tables and analyses. Where two or more ECG findings slot to the same visit interval, the most 'abnormal' results will be used, i.e. according to the following hierarchy: Abnormal-Clinically Significant > Abnormal – not clinically significant > Normal.

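### SAP 6.2.2 and 6.2.3 class a completer's Week 52 visit more than 35 days after the Week 48 dose as post-treatment, outside the data named for the SGRQ and FEV1 treatment-policy analyses, while SAP 6.2.6 says such measurements are kept.

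*SAP*

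**What the plan says.** SAP 6.2.2 sets the scope: "The analysis period defines the period of time over which exacerbations and efficacy assessments will be included in the on and/or off-treatment phases". For completers, the period ends at the "Earlier of Date of Week 52 visit or Date of last dose at Week 48 +35 days". The footnote derives the cap from the visit schedule: "date of last dose at week 48+35 days is defined as the upper bound of 7 days visit window for the date of last dose", counting 28 days plus the 7-day allowance.

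SAP 6.2.3 applies this period to visit-based efficacy (FEV1, SGRQ, ACQ and both response ratings). On-treatment and off-treatment both require a visit date no later than the period end. Post-treatment is "Visit Date > end of analysis period".

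SAP 4.3.2 describes the treatment-policy supplements for SGRQ and for FEV1 in the same words: "This analysis will include both on-treatment and off-treatment value". Post-treatment values are not named.

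SAP 6.2.6 states: "Measurements outside visit windows will not be excluded from analyses on any population". It also reports clinic visits by their nominal visit.

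SAP 4.4 sets the missing-data rules for the other endpoints. For ACQ-5 and SGRQ responders: "Any missing values at post-baseline visit will be included as non-responders". For the subject and clinician ratings, subjects without a Week 52 value "will be included in the analysis as category of significantly worse".

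**The concern.** The cap is the upper edge of the visit window, so the phase definitions set aside the kind of measurement that 6.2.6 promises to keep. A programmer who builds the analysis sets from the 6.2.3 flag and one who follows 6.2.6 would produce different Week 52 datasets, and both could cite the SAP.

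The patients concerned are completers who received the Week 48 dose and were then assessed late. The only intercurrent event in the SGRQ and FEV1 estimands is discontinuation of study treatment, and a late exit visit is not one. Neither the hypothetical nor the treatment-policy strategy gives a reason to discard their values. Week 52 is the target time point for both endpoints. A treatment-policy analysis that omits data collected from patients who stayed on treatment does not estimate what its name says.

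A further risk is conditional. The SAP does not say whether the phase flag also applies to the responder and rating analyses. If it does, a value that was measured would be handled as missing, and so as non-response or the worst rating category.

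**Working it through.** **1. The SAP's own figures.** The cap is 28 + 7 = 35 days (6.2.2 footnote). With first dose on Day 1 (day counting in 6.2.5), a Week 48 dose given 336 days later falls on Day 337, and 337 + 35 = Day 372. This is the full-follow-up day used in 6.2.4, so the cap is reproduced.

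**2. Classifying a completer dosed on Day 337.** Period end = min(visit day, 337 + 35). A visit is on-treatment if its day is at or before that end, and post-treatment otherwise.

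| Days from Week 48 dose | Visit day | Period end | Class |
|---|---|---|---|
| 21 | 358 | 358 | on-treatment |
| 28 | 365 | 365 | on-treatment |
| 35 | 372 | 372 | on-treatment |
| 36 | 373 | 372 | post-treatment |
| 42 | 379 | 372 | post-treatment |
| 60 | 397 | 372 | post-treatment |

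Off-treatment also requires a visit at or before the period end, so no visit beyond 35 days can reach it. The value is therefore outside the on- plus off-treatment set.

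**3. Can a visit that does not deviate be caught?** The schedule of activities gives Visits 3 to 15-2 a window of 7 days either side but does not state its anchor.
- If the window runs from the last dose, as the 6.2.2 footnote assumes, only out-of-window visits are affected.
- If it runs from first dose, a Week 48 visit 7 days early (Day 337 - 7 = 330) and a Week 52 visit 7 days late (Day 365 + 7 = 372) are both in window. They are 372 - 330 = 42 days apart, and the cap falls on Day 330 + 35 = 365, so the visit is post-treatment. Of the 15 x 15 = 225 pairs of in-window offsets, 28 give a gap above 35 days. That counts possibilities and does not forecast how often they occur.

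**4. Completers with no Week 48 dose.** Protocol 5.6 counts a patient who stops treatment early but attends Week 52 as a completer. Take a last dose on Day 141 and a Week 52 visit on Day 365.
- If the period ends at the visit, 141 + 28 = 169 < 365, so the visit is off-treatment and kept.
- If the cap runs from the actual last dose, the period ends on Day 141 + 35 = 176, so the visit is post-treatment.

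The SAP does not choose between these.

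**5. Primary endpoint.** For patients who did not stop treatment early, 6.2.3 counts events up to the period end, and the 6.2.4 offset runs to the same date. The cap costs some follow-up but does not mismatch events and time.

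**6. Illustration only, if the flag made late values missing in the responder analyses.** Assume 3% to 10% of visits are late and a true responder rate of 60%. An arm's reported rate then falls by 0.03 x 60 = 1.8 to 0.10 x 60 = 6 points. With equal lateness in both arms and assumed true rates of 60% and 40%, the 20-point difference shrinks by 0.03 x 20 = 0.6 to 0.10 x 20 = 2 points, towards no effect. None of these inputs is in the documents.

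**The case against.** The strongest reply is that 6.2.6 already settles the matter. The cap is a visit-window bound, and 6.2.6 says out-of-window measurements stay in and nominal visits are used. If it governs, nothing is lost. That is a fair reading, but no text ranks it above 6.2.3, and 6.2.3 expressly lists these endpoints. The result is undetermined, and that has to be resolved.

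Further objections limit how far the point reaches, and they stand:
- That the main MMRMs use on-treatment values is inferred from the hypothetical strategy and from supplements that add off-treatment data. The model text states no such limit.
- A reader might infer that late-assessed patients drop out of the SGRQ and FEV1 analyses. In an MMRM they stay in through their earlier visits and lose one value. Only the SGRQ ANCOVA sensitivity analysis, which uses observed data, would lose the patient.
- A reader might infer that favourable outcomes will be turned into the worst category. That needs a rule setting flagged values to missing, and SAP 4.4 contains none.
- A reader might infer that early stoppers who complete are exempt from the cap and so treated more generously. Their case is undefined (step 4).
- The planned pandemic listings (SAP 6.1.1) cover missed and remote visits, so they are no evidence about late ones. A false treatment difference would need lateness to differ by arm in a double-blind trial, and nothing in the documents suggests that.

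A limit on the on-treatment set is defensible in itself, since SAP 4.5.1 views each dose as covering 28 days. That does not justify removing the value from the treatment-policy analysis as well.

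**Conclusion.** The point holds as an internal contradiction that should be resolved. For a completer dosed at Week 48, the literal classification is certain: day 36 or later after that dose is post-treatment, and so outside the data named for the SGRQ and FEV1 treatment-policy analyses. Loss from the main MMRMs depends on their using on-treatment values. Recoding as non-response or worst category depends on the flag being carried into analyses for which the SAP does not mention it.

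The size is at most one Week 52 value per affected patient and endpoint in the MMRMs. The number of such patients cannot be derived from the documents, and the percentages in step 6 are illustrations. The documents do not support a claim that the primary result is distorted or that the treatment comparison is biased in favour of either arm.

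**What to change.** Before unblinding, amend SAP 6.2.2 and 6.2.3 in one of two ways:
- State that the 35-day cap applies to exacerbation counting only, and that 6.2.6 governs the nominal Week 52 visit for visit-based efficacy.
- If a limit on the on-treatment set is wanted, class a completer's later Week 52 visit as off-treatment, so that the treatment-policy analyses keep it.

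In either case, state in 4.4 that a measured Week 52 value is never treated as missing in the responder and rating analyses. Also define in 6.2.2 the end of the analysis period for completers with no Week 48 dose.

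The cost is a few sentences and one derivation change. The downside is small: a few values will come from beyond the nominal 28-day dose coverage. Under the first option there is no upper limit on how late such a visit may be. The second option avoids this for the on-treatment set.
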